5.0 ASSESSMENT OF EFFICACY AND SAFETY

5.1 Potential Risks of the Proposed Research to the Subject

The potential risks are low and rare; however, the following are possible complications or adverse reactions related to study participation. Participation in this study may involve some discomfort. These include feelings of frustration or embarrassment which may occur while completing the outcome measures.

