3.0 STUDY DESIGN

3.1 Overall Study Design

This is a 16-week single group study of PA promotion and monitoring along with its effect

on Neurological Health. Twenty Hispanic women seen at LAC/USC Neurology clinic will be referred to TWC and invited to participate in a physical activity (PA) study for 16 weeks. Participants will receive individualized Fitbit Charge activity monitors at baseline and instructed on its usage and maintenance. Adherence to activity monitor use and amount and level of PA will be determined. All assessments that include quality of life, exercise behaviors, and self-rated health and mood will be made at baseline and at 16 weeks at TWC. Educational/coaching will take place through (i) individualized instruction on exercise at baseline and at the end of week 4 at TWC and (ii) weekly calls from TWC to promote PA goal setting as well as Fitbit use. At the end of week 1, participants will be asked to return to the TWC to review instructions on Fitbit App use and to receive further education on the benefits of exercise through a brief Power Point presentation. Patient may also receive text messages throughout the study to remind them of upcoming appointments or deadlines. General Neurological Health status will be determined through use of Electronic medical records to determine hospital and outpatient clinic visits through the 16 weeks. At study completion, participants will be allowed to keep their Fitbit activity monitor and will receive a 3-month follow up post-study call to assess the continued usage of the Fitbit charge activity monitor and a quality of life questionnaire.

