3.4 Fitbit Charge HR2 Activity Monitor

Participants will be provided a Fitbit Alta HR and wall charger. Each participant will be given a unique ID# that will be assigned at baseline and used to set-up the Fitbit data acquisition. The Fitbit app will also be set up on their smartphone to allow self-monitoring of activity. The Fitbit device includes both an accelerometer and heart rate monitor and is capable of continuous measuring and storing data at up to a 1-second sampling rate for up to 5 days. Fitbit data will be passively downloaded through either a WiFi and/or smartphone connection to Fitabase. Fitabase (Fitabase, San Diego, Ca) is a research friendly application programming interface and comprehensive data management program that allows the device data from all users to be identified through a uniquely assigned ID# and transmitted in a secure fashion to the data acquisition and integration center.

The Fitbit Alta will be worn on the wrist every day during the course of the 16-week study. While the Fitbit is water resistant, participants will be asked not to wear the device while bathing or swimming. Participants will be instructed on self- monitoring, usage and maintenance of the Fitbit at the baseline visit. Participants will be monitored for Fitbit compliance by (i) weekly phone calls; and (ii) monitoring of passively downloaded Fitbit data through Fitabase data collection server. Further instructions will also be given 1 week into the study, to ensure proper compliance. Participants will be allowed to keep their Fitbit monitor at the end of the study. Follow-up phone call at 3-months post-study will assess continued use of the Fitbit activity monitor.

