3.5 Educational/Behavioral Coaching on Exercise (Lifestyle Redesign)

Participants will receive individualized goal setting and a guide to increase exercise at the beginning of the study (baseline) and at week four (week four visit) at TWC. The Occupational therapist (OT) will administer a well published approach for promoting PA called Lifestyle Redesign which addresses physical, psychosocial and environmental barriers to health and incorporate self-care strategies and goal setting. Coaching will be administered by a bilingual OT ([name]) and in language (Spanish or English) preferred by participant. Based on studies examining PA and brain health, the Occupational Therapist (OT) will guide the participant through a goal setting process for moderate to vigorous intensity of physical activity including a specific guide plan to achieve these goals of 10,000 steps per day and/or 150 minutes/week of moderate to vigorous activity. Participants will also receive weekly calls from the TWC (supervised by OT) to review PA and goal setting for each week over the course of the 16-week study.

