5.4 Adverse Event Reporting

All unexpected adverse events will be reported to the IRB. Serious adverse events (SAE) will be reported within 24 hours, first by phone and then followed by a written statement to the IRB. All serious adverse events will be followed to resolution and noted in the subject's chart. The following are defined as serious adverse events:

- Death
- Threat to life
- Inpatient hospitalization or prolongation of any existing hospitalization Persistent or significant disability/incapacity

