6.0 CLINICAL EVALUATIONS AND STUDY CALENDAR

Parameter	Screening Visit	Baseline Visit	Weeks 1-4	Week 4	Weeks 5-16	Week 16	Week 28
Demographic Information		Х					
Lifestyle Redesign Coaching		Х		Х			
Fitbit Charge Activity Monitor Instruction		Х					
Quality of Life (QOL)		Х				Х	
Spanish Acculturation		Х					
Brief Illness Perception Questionnaire (BIPQ)		Х				Х	
Patient Activation (PAM)		Х				Х	
Physical Activity Questionnaire		Х				Х	
FitBit Wear Technology Questionnaire						Х	
Phone Call for FitBit Use		Х	Х	Х	Х	Х	
Post-Study Phone Call on FitBit Use							Х

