7.0 DATA COLLECTION AND MONITORING

Data review will be ongoing by the study investigators to ensure scientific integrity of the study. A summary of study activity will be sent to the IRB annually with the continuing renewal submission. Quarterly reviews will take place to:

- determine whether all adverse events (if applicable) were appropriately reported
- check the Case Report Forms for legibility, accuracy and completeness
- validate the contents of the Case Report Forms against source
- oversee study progress and compliance
- verify that written Informed Consent and HIPAA authorization was obtained prior to patient's participation

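### The protocol coaches exercise but specifies no question about adverse events at any call or visit, so falls, injuries, exertional symptoms and non-county admissions depend on the participant volunteering them

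*Combined protocol and SAP*

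**What the plan says.** Section 3.5 has the occupational therapist set "goals of 10,000 steps per day and/or 150 minutes/week of moderate to vigorous activity", to be pursued in daily life over 16 weeks.

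The weekly calls are described in three places:
- Section 3.1: "weekly calls from TWC to promote PA goal setting as well as Fitbit use".
- Section 3.4: "Participants will be monitored for Fitbit compliance by (i) weekly phone calls".
- Section 3.5: "Participants will also receive weekly calls from the TWC (supervised by OT) to review PA and goal setting for each week".

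The section 6.0 calendar lists the in-study call as "Phone Call for FitBit Use" and has no adverse-event row at any time point.

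On harms, section 5.1 calls the risks low and rare and gives one kind of example: "These include feelings of frustration or embarrassment which may occur while completing the outcome measures". Section 5.2 places safety monitoring by certified staff at study visits. Section 5.4 states "All unexpected adverse events will be reported to the IRB", requires serious events to be reported within 24 hours, and counts inpatient hospitalization as serious.

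Sections 2.1.2 and 3.6.3 take hospital stays, emergency and urgent care visits and clinic visits from the LA County record as an outcome. Section 8.1 plans no summary of adverse events.

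**The concern.** Reporting rules act only on events that staff know about. Here the exercise takes place away from the centre, and the contacts that reach participants there are described without any enquiry about harm. A fall at home, a strained joint, dizziness on exertion or an admission to a hospital outside the county system could pass through all 16 weeks without entering a study record.

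Two things are at stake. The first is participant protection: an event that is not known cannot be reported or followed to resolution. The second is what the pilot can say about harm. Section 2.1 describes it as a source of feasibility and preliminary data for a larger application. If events are not sought systematically, a low count cannot be interpreted, and events nobody asked about cannot be recovered reliably later.

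**Working it through.** There is no planned figure to reproduce. The check is to take each contact or data source and ask whether the text requires anyone to enquire about adverse events.

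1. **Baseline, week 1, week 4 and week 16 visits** (sections 3.1, 3.5, 3.5.1, 6.0). Stated content is device instruction, education, coaching and questionnaires. Section 5.2 adds staff monitoring during the visit. No enquiry about events since the last contact is stated.
2. **Weekly calls** (sections 3.1, 3.4, 3.5, 6.0). Stated content is activity review, goal setting and Fitbit use or compliance. No adverse-event question is stated. Volume: 20 women × 16 weeks = 320 calls.
3. **The interval between on-site visits.** The longest is 16 − 4 = 12 weeks, or 12 × 7 = 84 days. Weekly contact continues throughout, so this is not a gap in contact. It is a gap in stated safety content: 12 calls per woman, 20 × 12 = 240 in all.
4. **Post-study call at week 28** (sections 3.1, 6.0). Section 3.1 gives it continued Fitbit use and quality of life; the calendar gives it Fitbit use only. Neither mentions adverse events.
5. **County medical record** (sections 2.1.2, 3.6.3). It would show admissions, emergency visits and urgent care at LA County facilities. No extraction schedule is given, and nothing links it to reporting under section 5.4. It would not show care at other facilities, or a fall or injury for which no county care was sought.
6. **Data review** (section 7.0). Review is ongoing, with quarterly checks that include whether adverse events were appropriately reported. This audits reports already made and does not elicit events.

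By type of event:
- County-treated events are retrievable from the record, at an unstated time.
- Non-county admissions and emergency visits have no stated route except spontaneous report.
- Falls, injuries and symptoms that led to no county visit have no stated route except spontaneous report, unless they occur during a visit.

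The first group is partly covered. The other two are the gap.

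**The case against.** The strongest case on the other side is this. The call descriptions state purposes and are not scripts, and a script with a safety question may exist outside the documents. A therapist-supervised review of activity could well bring up a fall that stopped someone walking. Entry is also screened: the referring neurologist is consulted about limitations, participants must walk unaided, and conditions that preclude exercise are excluded. The pilot has 20 women and draws no safety conclusion.

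Much of this stands as a limit on the point. The documents show that elicitation is not specified, not that staff would never ask. Screening lowers risk at entry, and no harm rate is known or alleged. But screening does not detect later events, and mention in conversation, with no duty to ask or log, would vary by caller and participant.

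A reader might infer more than the documents support:
- *That the 24-hour limit will be missed.* Section 5.4 does not say whether the clock starts at occurrence or awareness. If at awareness, late discovery is not a breach. If at occurrence, a weekly question could itself come up to 7 days late.
- *That quarterly review is too slow to detect events.* The item listed under "Quarterly reviews will take place to" is an audit of reporting, not a detection route, and section 7.0 also says data review is ongoing.
- *That only unexpected events are acted on.* The duty to report serious events carries no such limit. Because section 5.1 lists no activity-related harm, a fall would count as unexpected and be reportable once known.
- *That all admissions would be missed.* Those at county facilities are in the record.
- *That the pilot would claim to have shown safety.* No objective or analysis makes that claim.

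**Conclusion.** The point holds as a gap in ascertainment. An intervention that sets moderate to vigorous activity goals has reporting duties but no stated means of finding events, and its risk section does not mention the activity. It should be corrected, though it changes no planned estimate or test.

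Its extent is all of the roughly 320 scheduled calls and all on-site visits, none of which has a stated adverse-event question. The number of events that would be missed cannot be given, since the documents contain no event rate and no estimate of how often participants volunteer events.

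The conclusion assumes that the described content of calls and visits is what staff would follow, and that the county record is not used for real-time safety reporting, since no such use is stated. It does not rest on the removed consent pages. If a call script with a logged adverse-event question already exists, what remains is to cite it in the protocol, add the calendar row and align section 5.1.

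**What to change.** - In sections 3.1 and 3.5, state that at every weekly call and at the week 1, 4 and 16 visits staff ask and log one fixed open adverse-event question. Prompts should cover falls, injury, new symptoms during activity, and any emergency, urgent care or hospital visit at any facility.
- Add an adverse-event row to the section 6.0 calendar.
- State in section 5.4 that logged events enter its reporting process, and whether the 24 hours run from awareness.
- Check the log against the county record at data review under section 7.0.
- Reconcile section 5.1 with the exercise content of section 3.5.
- In section 8.1, add a descriptive table of all adverse events, expected or not, with the number of women affected and the number of calls and visits at which the question was asked. The last figure lets a reader tell no events from no enquiry.

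The cost is protocol and call-script wording, a simple log, and a short addition to calls already scheduled. No activity goal, eligibility criterion or planned analysis of the aims changes.

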5.2 Protection Against Risk

All participants will be monitored by certified personnel throughout study visit to ensure subject safety. Research data collected from the study will be kept confidential in secure locked cabinets located in the Wellness Center.

5.3 Potential Benefits of the Study to the Participants and Others

Participants could potentially benefit from education on how to incorporate PA into their lifestyles and from learning how the FitBit Alta HR activity monitor can help in doing so. Findings from this study could support policies for establishing the overall need to educate, prescribe, and make available exercise programs and facilities to participants within LA County, such as wellness centers within communities and county health facilities. As collaborators on this study we gain important knowledge regarding best practices for our participants with neurological disorders and insight regarding how to help support and monitor physical activity in our patient population.

5.4 Adverse Event Reporting

All unexpected adverse events will be reported to the IRB. Serious adverse events (SAE) will be reported within 24 hours, first by phone and then followed by a written statement to the IRB. All serious adverse events will be followed to resolution and noted in the subject's chart. The following are defined as serious adverse events:

- Death
- Threat to life
- Inpatient hospitalization or prolongation of any existing hospitalization Persistent or significant disability/incapacity

6.0 CLINICAL EVALUATIONS AND STUDY CALENDAR

Parameter	Screening Visit	Baseline Visit	Weeks 1-4	Week 4	Weeks 5-16	Week 16	Week 28
Demographic Information		Х					
Lifestyle Redesign Coaching		Х		Х			
Fitbit Charge Activity Monitor Instruction		Х					
Quality of Life (QOL)		Х				Х	
Spanish Acculturation		Х					
Brief Illness Perception Questionnaire (BIPQ)		Х				Х	
Patient Activation (PAM)		Х				Х	
Physical Activity Questionnaire		Х				Х	
FitBit Wear Technology Questionnaire						Х	
Phone Call for FitBit Use		Х	Х	Х	Х	Х	
Post-Study Phone Call on FitBit Use							Х

7.0 DATA COLLECTION AND MONITORING

Data review will be ongoing by the study investigators to ensure scientific integrity of the study. A summary of study activity will be sent to the IRB annually with the continuing renewal submission. Quarterly reviews will take place to:

- determine whether all adverse events (if applicable) were appropriately reported
- check the Case Report Forms for legibility, accuracy and completeness
- validate the contents of the Case Report Forms against source
- oversee study progress and compliance
- verify that written Informed Consent and HIPAA authorization was obtained prior to patient's participation

8.0 STATISTICAL CONSIDERATIONS

8.1 Statistical Methods

Preliminary analyses will begin with an examination of the distribution of key variables to assess their characteristics (means, standard deviations, skewness, and kurtosis), to provide descriptive statistics of the study population. Continuous measures will be tested for normality and homogeneity of variance. Non-normally distributed variables will be transformed to meet the normal distribution assumption for linear statistical models.

8.1.1 Specific Aim 1

The percent of valid days of FitBit use and length of time will be calculated. We will then examine the percentage of participants who had acceptable adherence as defined as over 5 or more days/week of valid use and 10 or more hours/day length of time.

8.1.2 Specific Aim 2

Given the small sample size power to detect significant associations between physical activity and number of hospital visits will be low. Therefore, these analyses will purely exploratory. We will generate change scores from baseline to 16 weeks for both physical activity variables by subtracting week 16 scores from baseline scores. We will use Poisson regression analyses to examine the associations between changes in physical activity with our dependent variable hospital visit outcomes. Poisson regressions will be fit to account for the fact that our dependent variable (hospital visits) is a count variable and non-normally distributed. All regression models will adjust for baseline level of physical activity. Significance level will be set at 0.05.

8.1.3 Specific Aim 3

All analyses described for aim 3 are also exploratory in nature as the proposed analyses will be underpowered to detect a significant association. Change scores in Quality of life, symptoms of anxiety and depression will be calculated by subtracting week 16 scores from baseline scores. Linear regression analyses will be run examining the associations between change in PA and our dependent variable of change.

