2.1 Primary Objective

This pilot study will provide feasibility on use of wearable technology for tracking and selfmonitoring PA as well as preliminary data to support our overall approach for promoting PA and improving disease status in a Hispanic women population. A larger application will be submitted to the NIH, DoD, or other federal agency focused on investigating the impact of PA on chronic neurological diseases in a diverse and inclusive Hispanic population in LA County.

2.1.1 Specific Aim 1

Specific Aim 1 establishes feasibility of this approach by measuring adherence and change in PA using a Fitbit Alta HR activity monitor in Hispanic women with chronic neurological diseases. Adherence will be determined through: (i) the average hours/day of use; and (ii) the length of time (percent of total study days) of usage throughout the 16-week study. Adherence defined as (i) 5 or more days/week of use and (ii) 10 or more hours of use during the day.

2.1.2 Specific Aim 2

Specific Aim 2 tests the hypothesis that an increase in physical activity will be correlated with a decrease in LA County (LAC) Facilities health care use (hospital and clinic visits). Physical activity will be assessed by change in either: (i) the average number of steps/week; and (ii) average time spent in sedentary, light, or moderate to vigorous intensity based on MET (metabolic expenditure) of physical activity/week. Methods: Changes in PA outcome metrics over the 16-week period will be correlated with the total number of hospital/outpatient clinic visits. Total hospital use will be determined through the LAC/DHS (Department of Human Services) electronic medical records and will include outpatient provider visits, emergency room and urgent care visits, total hospitalizations, and days spent in hospital.

2.1.3 Specific Aim 3

Specific Aim 3a tests the hypothesis that increase in physical activity is associated with an increase in the quality of life (QOL). Physical activity will be measured through: (i) the average number of steps/week; and (ii) average intensity of physical activity/week. QOL will be determined through measures of self-rated health and well-being. These Spanish validated surveys will include illness perception questionnaire and health and well-being questionnaire

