3.6 Primary Outcome Measures

3.6.1 Baseline Demographic Data

Following inclusion and exclusion and after obtaining informed consent, baseline demographic data will be obtained which will include age, recent healthcare visit frequency, medical history, medication, years of education, and tobacco use.

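### Aim 2's plain Poisson model makes no allowance for variance that differs from the mean, and leaves out the prior healthcare use collected at baseline (minor)

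*Combined protocol and SAP*

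**What the plan says.** Section 2.1.2 puts forward the hypothesis that "an increase in physical activity will be correlated with a decrease in LA County (LAC) Facilities health care use". The use to be counted covers "outpatient provider visits, emergency room and urgent care visits, total hospitalizations, and days spent in hospital", and the Methods text there relates PA change to the total over the 16 weeks.

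Section 8.1.2 gives the model: "We will use Poisson regression analyses to examine the associations between changes in physical activity with our dependent variable hospital visit outcomes". The reason offered is that visits are a count and not normally distributed. On covariates and level it says: "All regression models will adjust for baseline level of physical activity. Significance level will be set at 0.05". It also says that power is low and that the analysis is exploratory only.

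The one distributional remedy in 8.1 is: "Non-normally distributed variables will be transformed to meet the normal distribution assumption for linear statistical models". That concerns linear models, and nothing is said about the variance of counts.

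Section 3.6.1 lists among the baseline data "age, recent healthcare visit frequency, medical history, medication, years of education, and tobacco use". It gives neither a window nor a source for the visit frequency, and section 8 does not mention it again.

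**The concern.** Two omissions affect the same test.

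- **Variance.** Plain Poisson regression takes its standard error from the assumption that variance equals mean. Women with mixed diagnoses may differ widely in how often they attend. If so, the standard error is too small and the 5% test rejects too often. If most visits are regular scheduled appointments, the variance could be at or below the mean, and the test would be conservative.
- **Habitual use.** A woman who attended often before the study is likely to attend often during it. If habitual attenders also gain more, or less, activity than others, the PA coefficient picks up that link even when PA has no effect on visits. Baseline PA does not stand in for prior use.

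At stake is an exploratory association, not the feasibility result of Aim 1. But section 2.1 intends the pilot to supply preliminary data for a larger application, and a result below 0.05 could be carried into it.

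**Working it through.** **Inputs from the documents.** n = 20 (3.2); 16-week follow-up (3.1); level 0.05 (8.1.2; sidedness is not stated, two-sided assumed); model terms are an intercept, PA change and baseline PA. The plan gives no visit rate, dispersion or power figure, so there is no figure of its own to reproduce.

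**Assumptions.** Mean μ = 3 visits in 16 weeks (0.5 to 4 also tried); variance/mean ratio φ from 0.5 to 3; correlation ρ between a woman's log visit propensity and her PA change from 0.1 to 0.5; no true PA effect.

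**Step 1: large-sample size of the plain Poisson test.** If variance = φ × mean, the size is 2{1 − Φ(1.96/√φ)}. At φ = 1 this returns 5.0%, as it should.

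**Step 2: the same by simulation** at n = 20, μ = 3, baseline PA adjusted, no link between habitual use and PA.

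| φ | 1.96/√φ | Formula | Simulated |
|---|---|---|---|
| 0.5 | 2.77 | 0.6% | 0.7% |
| 1 | 1.96 | 5.0% | about 5% |
| 2 | 1.39 | 16.6% | 15–16% |
| 3 | 1.13 | 25.8% | 22–24% |

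For means from 1 to 4 the simulated rate at φ = 2 lies between about 13% and 16%.

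**Step 3: bias from leaving out habitual use.** With log-normal propensity, s² = ln(1 + (φ − 1)/μ). At μ = 3, φ = 2 this is ln(4/3) = 0.288, so s = 0.536. The spurious log rate ratio per SD of PA change is ρs = 0.3 × 0.536 = 0.16, a rate ratio of about 1.17 or its inverse, depending on direction.

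A 52-week prior count has mean 3 × 52/16 = 9.75, so its log carries noise variance of roughly v = 1/9.75 = 0.103. The bias left after adjustment is about ρsv/(s²(1 − ρ²) + v) = 0.161 × 0.103/(0.288 × 0.91 + 0.103) = 0.045. Simulation gives 0.05.

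**Step 4: rejection rates with that link** (μ = 3, φ = 2, no true effect). Ranges cover HC3 and Pearson-scaled quasi-Poisson SEs, each with a t reference, and repeat runs.

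| Analysis at ρ = 0.3 | Rejects |
|---|---|
| Plan as written | 27–29% |
| Dispersion-robust SE, no prior count | 10–13% |
| Dispersion-robust SE plus 52-week count | 4–6% |

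With HC3 and no prior count, ρ = 0.1 and 0.2 give 5% and 7%, so a weak link distorts little. At ρ = 0.5, HC3 gives 22% without the count and 6% with it.

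**Step 5: what adjustment does not mend.** If visit rates drift (correlation 0.7–0.85 between successive 16-week periods), HC3 at ρ = 0.3 rejects 10% unadjusted and 6–7% adjusted. If illness during the 16 weeks drives both visits and activity (assumed to be half the log-rate variance, correlation 0.3 with smaller gain), the bias is 0.12 with or without the prior count.

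**Step 6: choice of SE.** With the prior count at μ = 3, φ = 2, quasi-Poisson rejects 4.6% with intervals about 1.24 times the planned width; HC3 rejects 3.4% with intervals 1.43 times. At μ = 0.5, HC3 rejects about 2% and quasi-Poisson 6–8%. Neither is better throughout.

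**The case against.** The strongest reply is that 8.1.2 already calls the analysis exploratory and low-powered, that nothing in the documents shows overdispersion, and that no link between habitual use and PA change is documented. All of this is true, and it limits the point to a minor one. It does not dispose of it. A 0.05 level is still set, 2.1.2 still speaks of testing a hypothesis, and low power does not protect against an understated standard error or a confounder.

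A reader might infer more than the documents support:

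- *That the planned test is known to be anti-conservative.* No visit variance is given, and scheduled appointments could make it conservative.
- *That HC3 is the one right remedy.* Step 6 shows a trade-off. For rare outcomes neither method is established: at an assumed mean of 0.2, 52–70% of simulated trials had fewer than four women with any event.
- *That the change score is wrong.* It is formed "for both physical activity variables by subtracting week 16 scores from baseline scores", so a positive score is a fall in activity. That coding is stated and the sign follows from it. A reading note would help, but no wrong result is shown.
- *That the word decrease in Aim 2 calls for analysing change in use.* 2.1.2 Methods and 8.1.2 agree on the count over the study period, so this is wording.
- *That hospital days are to be summed with visits.* 8.1.2 speaks of outcomes in the plural, which allows separate analyses.

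**Conclusion.** The point holds as a minor one. That 8.1.2 names no dispersion allowance, and that the prior use collected under 3.6.1 enters no analysis, can be read directly from the text. The consequence is conditional. The planned test is near nominal if variance is close to the mean, conservative below that, and rejects roughly three times too often at an assumed ratio of 2 with a mean of 3 visits. Confounding by habitual use matters at an assumed correlation of about 0.3 or more and is small at 0.1–0.2; its true size and direction are unknown. Aim 1 is unaffected.

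**What to change.** In 8.1.2:

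1. Keep the Poisson mean model, but fix in advance one dispersion-robust standard error with a t reference on the residual degrees of freedom, and do not let the data decide a switch. Either HC3 or Pearson-scaled quasi-Poisson will do. In the cases simulated, HC3 is safer at low counts and quasi-Poisson gives narrower intervals at mean 3.
2. Add prior healthcare use, as log(count + 0.5), beside baseline PA. Define one look-back window in 3.6.1 for the visit frequency collected there, and take the count from the county electronic record if access to earlier records is authorised. Inclusion criterion 2 makes 52 weeks feasible. Section 3.1 describes only "use of Electronic medical records to determine hospital and outpatient clinic visits through the 16 weeks", so authorisation must be confirmed.
3. Report rate ratios with 95% confidence intervals, labelled exploratory. Report descriptively any outcome too rare to model, possibly admissions and hospital days.
4. State as a limitation that illness during the 16 weeks can affect both visits and activity and is not handled by the prior count.

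**Cost.** A few sentences of SAP text and, if authorised, one record look-back for 20 women. One residual degree of freedom is lost (20 − 3 = 17 becomes 20 − 4 = 16). At mean 3, intervals are about 1.1–1.3 times the planned width if counts are truly Poisson and about 1.2–1.4 times at ratio 2. With HC3 at mean 0.5 they are about 1.3 and 1.6–1.7 times. With no confounding, the prior count lowers the estimate's sampling SD by about 15% at mean 3, ratio 2, but raises it by 4% at mean 3, ratio 1, and by 9–18% at mean 0.5, ratios 1–2. Confounding by habitual use is reduced, not removed.
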